1.0 Objectives

1.1 Study Objectives

The primary aim is to determine whether breast cancer patients can be enrolled, randomized, retained, and comply with 6 months of aerobic exercise training; and, the feasibility of acquiring, managing and analyzing the cardiopulmonary fitness, cardiac function, quality of life, and tumor response data.

The secondary aim is to compare changes in hematological parameters (clinical blood biomarkers), cardiopulmonary fitness (VO₂max - stress testing), cardiac function (LVEF - echocardiogram), quality of life (surveys), and tumor response (tissue blocks from biopsy and surgical resection, MRI) in exercisers vs. control.

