1.2 Primary Study Endpoints

Study completion - feasibility

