1.3 Secondary Study Endpoints

n/a

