8.2 Sample size determination

N=10 intervention
N=10 control

Our intervention protocol is adapted from Hornsby et al. They report a final VO₂ of 1.6 ± 0.35 L/min in the intervention group and 1.2 ± 0.23 L/min in the control group. Thus, we are powered at 80% to see the same difference in VO₂ with 10 people per group assuming unequal variances. We have powered off of VO₂ as it is our physiological measure of intervention success per physiological adaptation.

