8.3 Statistical methods

Fisher's exact tests and χ^2 -tests will be used to examine between group differences in the overall proportion of patients experiencing treatment-related and training-related adverse events. A mixed-model repeated measures analysis of variance will be used to compare between group differences over time for outcome variables related to: cardiopulmonary fitness (VO₂max - stress testing), cardiac function (LVEF - echocardiogram), and tumor response (MRI). All efficacy outcomes will be assessed under the intention to treat principle. A two-sided significance level of 0.05 will be used for all statistical tests.

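### Sections 1.3 and 8.3 leave the efficacy comparisons without a named lead outcome: VO₂ sets the sample size but is not listed as an endpoint, and every test is run at 0.05

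*Combined protocol and SAP*

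**What the plan says.** Section 1.2 gives one primary endpoint, "Study completion - feasibility". The next entry, "1.3 Secondary Study Endpoints", is marked as not applicable.

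Section 1.1 nevertheless sets out between-arm comparisons. It begins "The secondary aim is to compare changes in hematological parameters (clinical blood biomarkers), cardiopulmonary fitness" and goes on to cardiac function, quality of life and tumor response, which makes five domains.

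Section 8.2 sizes the trial on one of these and gives the reason: "We have powered off of VO₂ as it is our physiological measure of intervention success per physiological adaptation".

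Section 8.3 names a mixed-model repeated measures analysis for three efficacy outcomes (VO₂max, LVEF and MRI tumor response) and Fisher's exact and χ² tests for adverse events. It then adds: "A two-sided significance level of 0.05 will be used for all statistical tests". Section 10.7 repeats the adverse event tests for safety review.

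Section 8.3 calls the mixed-model outcomes efficacy outcomes, and section 12.2 lists evidence of safety and efficacy among the benefits expected for future patients. No section ranks the outcomes, splits alpha, adjusts for multiplicity or labels the efficacy tests exploratory.

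**The concern.** The outcome that fixes the sample size has no entry in either endpoint section, and every comparison is given the same 0.05. If VO₂max showed no difference and LVEF or MRI response crossed 0.05, nothing in the plan would tell a reader that the second result carries less weight than the powered one.

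What is at stake is the secondary efficacy message of a 20-patient trial, not its primary conclusion. That message still matters: section 18.5 describes the study as a pilot whose monitoring procedures are to be developed for a national multi-site trial, so a chance finding could influence what that trial measures. Once the arms have been compared, a lead outcome chosen in advance can no longer be told apart from one selected because it was significant.

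**Working it through.** **1. The plan's own figure.** Inputs from section 8.2: "They report a final VO₂ of 1.6 ± 0.35 L/min in the intervention group and 1.2 ± 0.23 L/min in the control group", with 10 per group, unequal variances and a stated power of 80%. The two-sided 0.05 is from section 8.3.

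- Difference: 1.6 − 1.2 = 0.4 L/min.
- Standard error: √(0.35²/10 + 0.23²/10) = √(0.01225 + 0.00529) = 0.1324.
- Noncentrality: 0.4 / 0.1324 = 3.02.
- Satterthwaite df: 0.01754² / (0.01225²/9 + 0.00529²/9) = 15.6.
- Welch power from the noncentral t distribution: 80.8%. A simulation of 200,000 trials gives 80.5%.

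The stated 80% reproduces. It holds for VO₂ alone, at an unadjusted 0.05, with 10 women analysed per group.

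**2. Chance of at least one false positive.** With no true effects and k independent tests at 0.05, this is 1 − 0.95^k. For correlated outcomes I simulated equicorrelated normal test statistics. The correlations are assumptions, because the documents give none.

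| Set of outcomes | k | Independent | Correlation 0.5 | Correlation 0.8 |
|---|---|---|---|---|
| Efficacy outcomes named in 8.3 | 3 | 1 − 0.857 = 14.3% | about 13% | about 10% |
| Domains in 1.1, one test each | 5 | 1 − 0.774 = 22.6% | about 18% | about 13% |

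The first row is what section 8.3 specifies. The second applies the 0.05 rule to quality of life and hematology as well, although section 8.3 names no analysis for either. Testing each questionnaire (7.2.7) or blood marker (7.2.2) separately would raise the figure, but the documents do not say how many such tests there would be.

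**3. What each remedy does to VO₂ power.**

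- VO₂max as the only efficacy test at 0.05: power stays at 80.8% with 10 per group.
- Bonferroni over the three outcomes in 8.3 (0.05/3 = 0.0167): power falls to 63.5%. Reaching 80% takes 14 per group (13 gives 79.1%, 14 gives 82.8%).
- Bonferroni over the five domains (0.05/5 = 0.01): power falls to 54.9%.

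Naming a single lead outcome is therefore the remedy that fits the planned 20 women.

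**The case against.** The strongest reply is that this is a feasibility pilot. No efficacy p-value can satisfy the primary endpoint, and formal error control over secondary outcomes in 20 patients is partly a matter of taste. The first part stands, and it limits the point to secondary efficacy statements. A reader might infer that the trial could be declared positive on whichever outcome reaches 0.05; section 1.2 rules that out.

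A reader might also infer that VO₂ has no standing at all. That goes too far. Section 1.1 names it in the secondary aim and section 8.2 gives it the leading physiological role. What is missing is the formal label, and a statement of what the other tests are for.

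Third, a reader might count about eleven tests: VO₂max, LVEF, MRI, tumor infiltrating lymphocytes, hematology, four questionnaires and two adverse event tests. That gives 1 − 0.95^11 = 43%, close to an even chance. The documents do not support the count. Section 8.3 states no between-arm test for six of the eleven (the lymphocytes, hematology and the four questionnaires), and the adverse event tests are safety comparisons, not routes to an efficacy claim. The missing analyses for quality of life and hematology are a separate gap.

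The reply does not remove the core. The plan foresees efficacy conclusions, applies 0.05 to all tests, and neither ranks the outcomes nor calls any of them exploratory.

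**Conclusion.** The concern holds for the secondary efficacy conclusions. Sections 1.1, 1.3, 8.2 and 8.3 do not agree on which outcome, if any, carries them. For the outcomes that section 8.3 names, the chance of at least one false positive is 14.3% under independence and about 10% to 13% at assumed correlations of 0.8 to 0.5, against the 5% attached to each single test. For the five domains it is 22.6% under independence, assuming one test per domain. These figures assume no true effect on any outcome and tests that hold their nominal level.

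The feasibility conclusion and the sample size calculation are not affected. The correction is worth making before the arms are compared, because it changes a stated rule and what the trial may claim, and it follows the choice of VO₂ already made in section 8.2.

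**What to change.** In section 1.3, replace the not-applicable entry with the outcomes of the secondary aim. Name predicted VO₂max, compared between arms at the final visit, as the single key secondary efficacy endpoint. In section 8.3, replace the sentence on the significance level with:

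> Among efficacy outcomes, only VO₂max is tested at two-sided 0.05. All other efficacy, quality-of-life, hematological and biomarker comparisons are exploratory and are reported as estimates with 95% confidence intervals, without claims of significance. The adverse event tests in 8.3 and 10.7 are kept as safety comparisons.

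The last sentence keeps section 8.3 consistent with section 10.7. No false discovery rate procedure is needed for the blood markers: section 8.3 plans no between-arm test of them, and such a procedure would conflict with reporting them without significance claims.

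The cost is an edit to two sections, with no added patients or data. The sponsor gives up significance claims for the other outcomes, for which the protocol states no power. The 80% power for VO₂ at 10 per group is unchanged.

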9.0 Confidentiality, Privacy and Data Management

See the Research Data Plan Review Form

10.0 Data and Safety Monitoring Plan

10.1 Periodic evaluation of data

Participant's medical records will be monitored at every infusion appointment.

10.2 Data that are reviewed

Laboratory reports and clinician progress notes.

10.3 Method of collection of safety information

Case report form to document monitoring and results of monitoring.

10.4 Frequency of data collection

Every cycle of chemotherapy.

10.5 Individuals reviewing the data
Oncology fellow, and [name].

10.6 Frequency of review of cumulative data
We will review following the mid point of enrollment (10 women randomized), and following the completion of half of the cohort (10 women finished the study).

10.7 Statistical tests
Fisher's exact tests and χ^2 -tests will be used to examine between group differences in the overall proportion of patients experiencing treatment-related and training-related adverse events.

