12.2 Potential Benefits to Others

The information obtained from this research study may benefit future breast cancer patients by demonstrating safety and efficacy of an at home aerobic exercise intervention. Such an intervention may improve cardiopulmonary fitness, cardiac function, and tumor response to chemotherapy. Information obtained in this study may help us increase the effectiveness of neoadjuvant chemotherapy while also decreasing cardiotoxic side effects.

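### The only planned analysis of adverse events is a significance test at 10 women per arm, which cannot support the safety statement anticipated in 12.2

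*Combined protocol and SAP*

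**What the plan says.** Section 8.3 and section 10.7 carry the same sentence on adverse events: "Fisher's exact tests and χ^2 -tests will be used to examine between group differences in the overall proportion of patients experiencing treatment-related and training-related adverse" […]. Section 8.3 adds: "A two-sided significance level of 0.05 will be used for all statistical tests". Which of the two tests decides is not stated.

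The arms are small ("N=10 intervention", and the same number of controls). Section 8.2 sets that size on fitness alone: "We have powered off of VO₂ as it is our physiological measure of intervention success per physiological adaptation". The plan gives no expected adverse event rate, no excess of harm worth detecting, no harm margin, no interval estimate for adverse events and no power for harm.

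Safety is absent from the aims in 1.1. The primary endpoint in 1.2 is feasibility, and 1.3 lists no secondary endpoints. The safety wording comes in 12.2, among possible benefits to others, where the study's information may help future patients by "demonstrating safety and efficacy of an at home aerobic exercise intervention".

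Section 7.2.6 asks controls to keep their usual activity and not to begin a new exercise programme. Section 18.4 names musculoskeletal injuries and cardiopulmonary emergencies as the events monitored in both groups.

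**The concern.** A test of no difference can signal harm when it rejects. When it does not reject, it says little unless the sample was large enough to make rejection likely under a harm that matters. Here the sample was sized for VO₂, and no one has stated what the adverse event comparison could detect. If the result is p > 0.05, which is likely with 10 per arm even under a sizeable excess, the report will contain no figure showing how much harm remains compatible with the data.

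This matters because 12.2 foresees a statement about safety, and small trials do get cited that way. Section 2.1 itself reports a 20-woman trial of supervised training, the same total size as this one, as having found the training safe. Section 18.5 says that the monitoring and audit procedures will be developed further for a national multi-site trial, so the adverse event summary from this pilot is likely to be carried forward.

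**Working it through.** **Inputs from the documents.** 10 women per arm (8.2); two-sided 0.05 (8.3); Fisher's exact and chi-square tests (8.3, 10.7). Withdrawn women are not followed (3.3.2), so 10 per arm is a best case.

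**Assumed inputs.** The documents give no adverse event rates for women in neoadjuvant chemotherapy. I take control risks of 0–30% and excesses of 20 and 30 percentage points, with one larger case for contrast.

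**Step 1: the plan's own power figure.** Section 8.2 states 80% power from: "They report a final VO₂ of 1.6 ± 0.35 L/min in the intervention group and 1.2 ± 0.23 L/min in the control group". Standard error = √(0.35²/10 + 0.23²/10) = √0.01754 = 0.132. Noncentrality = 0.4/0.132 = 3.02. The Welch t-test on about 15.6 degrees of freedom then has power 80.8%. The stated figure reproduces, but it concerns VO₂ only.

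**Step 2: what the tests need in order to reject.**
- No events in 10 controls: Fisher gives p = 0.087 for 4 of 10 exercisers and p = 0.033 for 5 of 10, so 5 are needed. Uncorrected chi-square gives p = 0.060 for 3 and p = 0.025 for 4, so 4 are needed.
- One event in 10 controls: Fisher gives p = 0.14 for 5 of 10 exercisers and p = 0.057 for 6 of 10, so 7 are needed (p = 0.020).

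**Step 3: probability of missing a true excess.** Miss rate = 1 − Σ Bin(a; 10, p_E) × Bin(b; 10, p_C), summed over all tables with a > b and p ≤ 0.05. Here a and b are the numbers of women with an event in the exercise and control arms.

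| Control v exercise risk | Fisher | Uncorrected chi-square |
|---|---|---|
| 10% v 30% | 94.3% | 85.7% |
| 20% v 40% | 94.2% | 87.0% |
| 30% v 50% | 94.6% | 87.4% |
| 0% v 30% | 85.0% | 65.0% |
| 10% v 40% | 84.8% | 70.9% |
| 20% v 50% | 86.8% | 74.6% |
| 30% v 60% | 87.7% | 75.3% |
| 10% v 50% (40 points) | 70.5% | 52.9% |

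One 20-point case lies just above these ranges. For 0% v 20%, Fisher rejects only with 5 or more events in 10 at a risk of 0.2, which has probability 0.033, so it misses 96.7%. Chi-square misses 87.9%.

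**Step 4: what estimation would show instead.**
- Clopper–Pearson, 0 of 10: the two-sided 95% upper limit is 1 − 0.025^(1/10) = 30.8%. The one-sided 95% bound is 1 − 0.05^(1/10) = 25.9%.
- Clopper–Pearson, 1 of 10: two-sided 95% interval 0.3% to 44.5%.
- 3 of 10 v 1 of 10: Fisher p = 0.58. The risk difference is 20 points. The Wilson limits are 10.8% to 60.3% and 1.8% to 40.4%. The Newcombe limits are therefore 0.20 − √((0.300 − 0.108)² + (0.404 − 0.100)²) = −0.16 and 0.20 + √((0.603 − 0.300)² + (0.100 − 0.018)²) = 0.51. The p-value alone would hide that an excess of about 50 points is still compatible with the data.

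**Step 5: training-related events.** Under 7.2.6 controls are asked not to begin an exercise programme, so their count of such events is close to zero by design. A between-arm test then mostly asks whether the exercise-arm rate differs from zero. The useful quantity is that rate and its interval.

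**The case against.** The strongest reply is that this is a feasibility pilot that makes no safety claim. Much of that stands. Safety is in neither aim, and the phrase in 12.2 describes a possible benefit. A reader might infer that the trial sets out to prove safety, or that p > 0.05 is its criterion for it. The documents contain no such aim or rule; 8.3 and 10.7 say only that differences will be examined.

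The test is also not the only safety provision. Records are reviewed at each infusion (10.1–10.4), cumulative data are reviewed twice (10.6), events are graded by CTCAE and judged for relatedness (18.4), and 7.2.7 adds an adverse effects survey and an injury questionnaire. These deal with individual cases, but they do not say what the trial can conclude about rates.

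A reader might also infer that the test is run at the cumulative reviews. Section 10.6 gives their timing ("We will review following the mid point of enrollment (10 women randomized" being the first) but no method, and 10.7 does not say when the test is done.

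The miss rates rest on assumed risks, and the higher range belongs to Fisher. The documents also give no support for a 20–30 point rise in cardiopulmonary events. Section 11.0 quotes 2 nonfatal cardiovascular events in 375,000 hours of exercise. Ten women at 75 minutes a week for 24 weeks accrue 10 × 1.25 × 24 = 300 hours, or 300 × 2/375,000 = 0.0016 expected events. That source is a general activity centre and not women in chemotherapy, but it is the only such figure given. The scenarios are more plausible for musculoskeletal events.

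Nor should the point be extended to LVEF, which 8.3 treats as an outcome in a repeated-measures mixed model.

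Finally, intervals at this size are wide and may not change a pilot decision. That is so, but the width is what the reader needs to see.

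**Conclusion.** The point holds in a limited form. The one planned statistical analysis of adverse events cannot support a statement that the programme is safe, and 12.2 anticipates such a statement. For excesses of 20 to 30 points, the miss rate is about 85–95% with Fisher and about 65–87% with uncorrected chi-square. It assumes control risks of 0–30% and full retention of 10 per arm. At a 40-point excess (10% v 50%) the figures fall to 70.5% and 52.9%, so the size depends on the scenario and the test. The conclusion that non-significance is uninformative holds throughout the 20–30 point range. For training-related events the between-arm comparison adds little under any rate, because of 7.2.6.

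This is a gap in analysis and reporting. It does not show that the plan will misread its results, and it affects neither the feasibility aim nor the VO₂ sample size. It is worth correcting because the correction is cheap and changes what the trial can say about harm.

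**What to change.** In 8.3 and 10.7, make estimation the basis of the adverse event summary:
- For each arm and each monitored event type, report the number and proportion of women affected, with an exact (Clopper–Pearson) two-sided 95% interval.
- For events that can occur in both arms, report the risk difference with a 95% interval, for example Newcombe's.
- For training-related events, report the exercise arm's rate and interval rather than rely on the comparison.
- Keep the tests, if wanted, as descriptive, and state that a non-significant p is not evidence of safety.

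In 12.2, replace the claim of demonstrating safety and efficacy with one of providing preliminary safety and efficacy data.

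The cost is a few sentences in three sections and a few lines of analysis code. No new patients, data or procedures are needed. The drawback is a more modest safety statement.

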10.8 Suspension of research
n/a

11.0 Risks

The risk of maximal cardiopulmonary exercise testing is approximately 1 nonfatal event in 10,000 maximal treadmill tests and only 1 fatal cardiac complication in over 70,000 maximal exercise tests. Major complications of exercise testing include death, fatigue, myocardial infarction, arrhythmia, hemodynamic instability, and orthopedic (bone, muscle, tendon, joint) injury. Skin irritation may occur at the sites where electrodes were placed.

The risk of an exercise training induced CV event is 2 nonfatal CV events in 375,000 subject hrs of exercise, or about 1 event per 1.7 million walk/jogging miles, based on a large Dallas, TX physical activity center study. Cardiovascular risks associated with exercise training are: abnormal heart rate or rhythm, heart attack, stroke, or even death.

Other risks of exercise training include: muscle pain, muscle strains/sprains, joint pains (such as hip, knee, ankle or foot pain), fatigue, risk of fall resulting in trauma/fracture.

There are no serious risks associated with transthoracic echocardiography. It is possible that subjects may experience mild, temporary discomfort from the ultrasound probe being pressed against the chest or from lying in the recumbent position for the duration of additional imaging.

There are no medical risks associated with filling out surveys, however a woman may become uncomfortable providing personal information. Any questions that make them uncomfortable can be skipped.

No additional blood draws will be done outside of standard clinical care.

There is a risk of loss of confidentiality if your medical information or your identity is obtained by someone other than the investigators, but precautions will be taken to prevent this from happening.

12.0 Potential Benefits to Subjects and Others

12.1 Potential Benefits to Subjects

Participants randomized to the intervention whom comply with study procedures will increase their cardiopulmonary fitness and decrease their risk for cardiovascular disease.

12.2 Potential Benefits to Others

The information obtained from this research study may benefit future breast cancer patients by demonstrating safety and efficacy of an at home aerobic exercise intervention. Such an intervention may improve cardiopulmonary fitness, cardiac function, and tumor response to chemotherapy. Information obtained in this study may help us increase the effectiveness of neoadjuvant chemotherapy while also decreasing cardiotoxic side effects.

13.0 Sharing Results with Subjects

We will tell participants in the intervention arm if they increased their fitness level following completion of exercise testing. We will also tell HER2(-) participants clinically relevant results of their research echocardiogram.

14.0 Subject Stipend (Compensation) and/or Travel Reimbursements

Subjects in the control arm will receive DVDs and the exercise binder following the completion of final testing. Subjects in the intervention arm will receive DVDs and intervention materials (exercise binder and exercise logs) prior to starting chemotherapy. No other compensation will be given for time or travel.

15.0 Economic Burden to Subjects

15.1 Costs

None

15.2 Compensation for research-related injury

It is the policy of the institution to provide neither financial compensation nor free medical treatment for research-related injury. In the event of injury resulting from this research, medical treatment is available but will be provided at the usual charge. Costs for the treatment of research-related injuries will be charged to subjects or their insurance carriers.

